4.6 Benefit-Risk Considerations

During the study, every patient will only use the FeetMe® Monitor device and patients in the FeetMe rehabilitation groups will use FeetMe Rehabilitation applications as well.

The current generation of the insoles, which is the improvement of the previous generations, have been on the market since 2019 and have been used by approximately 2530 people. Neither this nor previous generations of the insoles have had device-related adverse events reported. The insoles have been used

in a variety of populations. In a validation study, the gait parameters of 25 healthy volunteers aged 20 to 77 years were analysed to compare the FeetMe® insoles against the GAITRite® mat reference. The devices were concluded to be equivalent in estimating the mean and variability of gait parameters (Jacobs et al., 2021). The system was also validated against the GAITRite® with 205 Multiple Sclerosis patients (Domínguez et al., 2020) and 29 Stroke patients (Farid et al., 2021). In these studies, patients had to walk 8 meters (25 Foot Walk Test) multiple times. Agreement between the devices was almost perfect in both populations. Tests with 19 adults older than 65 years in good perceived health status were carried out during single- and motor-cognitive dual-task trials while outdoor walking, mimicking real-life situations. Patients had to perform 3-minute walking tests outdoors, altogether four times. The device proved to be capable of reliably capturing between condition differences in gait parameters transparently and accurately studying ecological walking activities. Additionally, it received an excellent usability feedback (Lunardini et al., 2021). To characterise and compare gait patterns in relapsing-remitting MS and secondary-progressive MS, 141 patients were enrolled in a study where they had to perform three gait assessments, a 6MWT, a 2-minute walk test and a 25 Foot Walk Test (Granja et al., 2019). The insoles were likewise successfully used in a spastic hemiparetic patient with foot drop (David et al., 2019).

Furthermore, the insoles have already been used together with the FeetMe Rehabilitation application as remote rehabilitation service in Parkinson's disease patients. A one month pilot study to test this solution was conducted with 13 PD patients during the first lockdown period of the COVID-19 pandemic. Patients showed a very high compliance, measured by the amount of practice time versus the prescribed practice time and reported overall satisfaction with the program. Patients were further given the option to continue with the rehabilitation program and the majority chose to do so, completing three month (9 patients) and six months (7 patients) of remote rehabilitation. Importantly, a positive trend was observed in the patient's quality of life (Laplanche et al, 2021). There have been several other individual use cases where the solution was successfully deployed and an initiative where the FeetMe solution will be used by thirty PD patients with apomorphine pump is currently being conducted. Further details are provided in the Investigator's Brochure.

In the current study, during the in person study visits on site well established gait measurements (6MWTs and the MiniBESTest) will be conducted using the insoles. The testing procedures will follow standard testing instructions. These assessments will be conducted under the direct supervision of a health care professional and therefore are not considered to put the study population at any risk.

Patients in their home will either use only the insoles or the combination of the insoles and the Rehabilitation application. Patients can encounter a minimal residual risk while using the insoles which can originate from inappropriately using the charging device by using an incompatible charging module. This risk is minimised by providing all patients with an adapter compatible with their location and clear instructions in the user manual. Regarding the application, theoretically it may occur that the instructions, movement targets during the exercises or the biofeedback would not be properly displayed on the patient' smartphone screen, resulting in movements of potentially excessive amplitude and consequently in loss of balance. This risk is considered to be at an acceptable level by the Sponsor as it has been reduced to the minimal technically possible level during the development of the software and will be further mitigated by adequate training of patients before use and regular follow-up.

The current population assessed is not considered to be more compromised and therefore at higher risk compared with patients who have previously used the insoles and the smartphone application without device-related side effects. Additionally, it is ensured throughout the eligibility criteria that the study population is cognitively and physically capable of respectively understanding and executing the prescribed rehabilitation. Regular follow-up calls are also planned to verify that patients are using the solution both safely and efficiently.

Overall, any residual risk is outweighed by the benefit patients are expected to have by using the FeetMe Rehabilitation solution.

4.7 Non-investigational Medical Device

The investigational site will be provided their own FeetMe® Monitor insoles together with the FeetMe® Evaluation application as a back-up (e.g.: for instances when a patient forgets their own device). During the on-site visits the gait assessments might therefore be recorded using these devices. Patients on the CPt arm will be provided the Evaluation application along their insoles in order to download the data during their remote gait monitoring. As these actions are within the intended use the devices, they are not considered as investigational medical devices in the study.

5 STUDY OBJECTIVES AND ENDPOINTS

Table 5.1 Study Objectives and Endpoints

Primary Objective	Primary Endpoints				
To evaluate the efficacy of FeetMe home-based rehabilitation program compared to conventional physiotherapy at Week 12 in PD patients assessed by gait velocity.	Change from baseline to Week 12 (Visit 3) in gait velocity (cm/s) assessed during the 6 Minutes Walk Test (6MWT).				
Key Secondary Objective	Key Secondary Endpoint				
To evaluate the efficacy of FeetMe home-based rehabilitation program compared to conventional physiotherapy at Week 12 in PD patients assessed by stance time variability.	Change from baseline to Week 12 (Visit 3) in Stance Time Variability assessed during the 6 Minutes Walk Test (6MWT).				
Secondary Objectives	Secondary Endpoints				
To evaluate the efficacy of FeetMe home-based rehabilitation program compared to conventional physiotherapy at Week 12 in PD patients assessed	• Rate of falls at Week 12 (Visit 3) based on the results of the falls diary.				
 by: rate of falls standard gait and balance exercises 	• Change from baseline to Week 12 (Visit 3) in the asymmetry of the swing duration assessed during the 6 Minutes Walk Test (6MWT).				
MDS-UPDRS Part IIIquality of life	• Change from baseline to Week 12 (Visit 3) in the MiniBESTest.				
	• Change from baseline to Week 12 (Visit 3) in MDS-UPDRS part III sub-score.				
	• Change from baseline to Week 12 (Visit 3) the results of the Parkinson Disease Questionnaire (PDQ-39)				
Exploratory Objectives	Exploratory Endpoints				

• To explore the long term efficacy home-based rehabilitation program to conventional physiotherapy in pa	of FeetMe compared atients who	Rate of falls at Week 24 based on the results of the falls diary. Change from Baseline to Week 24 (Visit 4)
continue to Week 24		and from Week 12 (Visit 3) to Week 24 in:
• To explore the maintenance of the 3 months in patients who stop phy at Week 12.	effect after vsiotherapy	- Gait velocity (cm/s) assessed during the 6MWT
 To explore the efficacy in patients of from one treatment to the other at X 	who switch Veek 12	- Stance Time Variability assessed during the 6MWT
	V CCR 12.	- Asymmetry of the swing duration assessed during 6MWT
		- the Mini-BESTest
		- MDS-UPDRS Part III sub-score
		- the results of the PDQ-39
	•	Change from Baseline to Week 12 (Visit 3) and to Week 24 (Visit 4) and from Week 12 to Week 24 in the:
		- gait parameters measured by the FeetMe Monitor during the 6MWTs other than ones of the primary and secondary endpoints
		- gait parameters measured by the FeetMe Monitor during remote gait monitoring
		- results of the pain VAS
		- results of the Parkinson Disease Sleep Scale 2 (PDSS2)
		 results of the Clinical and Patient Global Impression of Severity scales (CGI/PGI- S)
		- results of the Clinical and Patient Global Impression of Improvement scales (CGI/PGI-I)
		- results of the MDS-UPDRS I, II and IV sub scores
To explore the compliance with acceptability, and patient's e throughout the study	training, Ac ngagement phy	ctual versus prescribed time spent on hysiotherapy
To explore the satisfaction with the ser-	vice Re sat	esults of the Patient and Investigator tisfaction questionnaire
To evaluate the safety of FeetMe h rehabilitation program.	ome-based Nu pla	umber of device and clinical investigational an procedure related adverse events.

5.1 Appropriateness of Measurements

Several studies support the clinical utility of using gait parameters to provide insight into the efficacy of rehabilitation. Gait velocity appears as an outcome measure for therapies such as the LSVT BIG (Millage et al, 2016) or DBS (Roger et al, 2016) and for almost all alternative forms of physical exercises aiming at improving mobility of PD patients. In the European Physiotherapy Guideline for Parkinson's Disease walking speed is graded as a "critical outcome", with an importance score of 8.6 over 10 (Keus et al, 2014). The FeetMe devices provide the opportunity to objectively and reliably measure this important outcome.

During a discussion between the HAS and the Sponsor in February 2021, the agency has supported the proposal of using gait velocity as a primary endpoint for this study. The reason being that gait velocity is shown to correlate with several other aspects of disease, e.g. risk of falls or quality of life.

In one study conducted on individuals aged 70 and older, each 10 cm/s decrease in gait speed was associated with a 7% increased risk for falls (Verghese et al., 2009). Participants with slow gait speed (\leq 70 cm/s) had a 1.5-fold increased risk for falls compared with those with normal speed. Since these falls occur during walking, apart from reduced speed, gait disturbances such as changes in stride time variability, or medio-lateral symmetry are also associated with falls. Therefore, walking speed can be an optimal proxy measure for evaluating fall risk in PD patients (Creaby and Cole, 2018; Paul et al., 2013; Rodríguez-Molinero et al., 2019; Verghese et al., 2009).

For better interpretability of the change in velocity the key secondary outcome measure of stance time variability is introduced. This parameter is described to be related to balance and motor control (Rennie et al, 2020). It is expected that a quantitative change in the gait (i.e.: speed) complemented with the quality of the change (i.e.: stance time variability) will reflect the stability of the walk and will best depict the impact of the rehabilitation therapy.

Additionally, a large pool of gait parameters will be available to further characterise the motor functions of the patients. The standards in clinic tests will be complemented with the special feature of the FeetMe devices which allows the remote continuous gait monitoring within home settings. This will provide a new pool of evidence thanks to the digital technology that can be newly adopted within this population. The non-gait-based endpoints are there to provide a holistic view on the status of the patients as they represent the clinically relevant domains of the non-motor aspects of the disease. They will be looked at independently and in relation to the various gait parameters.

6 INVESTIGATIONAL PLAN

6.1 Study design and rationale

This is a multicentre, controlled, randomised in two parallel groups, open label study. The study will enroll 150 patients over approximately 18 months and 6 investigational sites.

Having multiple centres enrolling patients will not only maximise the capacity of recruitment but will allow for the evaluation of differences represented by geographical imbalances in the physiotherapy practices across France.

Patients who are found eligible and consent to participate will be randomised either on the conventional physiotherapy or on the FeetMe arm in a 1:1 ratio. Due to the set-up of the FeetMe program (i.e.: personal follow-up of the patients by an APA and the difference in the device needs between the two groups) and the obvious difference in the treatments, a blinded design is not possible. Nevertheless, the objective nature of the primary and main secondary endpoints measured by digital technology and the patient reported nature of most of the remaining outcome measures minimise any potential biassing effect originating from the open label design. Additionally, the final analysis will be performed by a independent blinded statistician.

The equal allocation of patients is maintained during the Primary Intervention Period (from the Baseline Visit till Visit 3) up to the primary endpoint evaluation at Week 12. It is in line with the duration of the FeetMe rehabilitation program. The program is built based on several regulatory recommendation including the HAS and the WHO and expert opinions suggesting that rehabilitation trainings typically show benefit after ten weeks. Additionally, most of the published data supports this duration together with the list of interventions analysed in the European Physiotherapy Guideline for Parkinson's Disease (Keus et al, 2014) where the median duration of the programs is eight weeks. The timing of the primary endpoint at Week 12 is adopted to this standard duration of an intensive rehabilitation therapy off approximately 3 months.

After the Primary Intervention Period patients will be offered to chose how to proceed i.e.: to continue on their original allocation, to switch arms or to stop treatment. In any case the patients will remain in the study until the week 26 EOS visit. The number of patients on the arms at this point will not be controlled and the data gathered will be exploratory in nature. This design is expected to:

- provide the opportunity to those patients on the conventional physiotherapy arm who will not find a therapist during the study to get access to treatment by switching to FeetMe;
- assess the ratio of the willingness to continue on the FeetMe arm in comparison to the conventional arm;
- assess the maintenance of the treatment effect in patients who decide to stop;
- compare efficacy of the two treatment within the same individual who decides to switch;
- compare the long-term efficacy of the two treatments at 6 month in patients who continue on their original allocation.

Based on the emerging data, the Sponsor may decide to open an extension phase, where all participants have the option to take part or prolong their participation in the FeetMe rehabilitation program. Such extension to this study may be offered to all patients, contingent on the Sponsor's decision to implement it and could be described in a separate document.

In case study conduct will be compromised by the COVID-19 pandemic a contingency plan will be provided in a clinical investigational plan addendum.

FeetMe reserves the right to temporarily suspend or prematurely discontinue the study at any time. The study may also be terminated prematurely at any time when agreed by both the Investigators and the Sponsor as being in the best interest of the patients. In terminating the study, FeetMe and the Investigator will ensure that adequate consideration is given to the protection of the patients' interests. If the study is prematurely terminated or suspended, FeetMe will inform the Investigators/institution and the regulatory authorities and IEC in accordance with applicable regulatory requirements. In addition, arrangements will be made for the return of all study material provided by the Sponsor.

CIP Number 2023-A00150-45 Final version 0.2

CONFIDENTIAL May 2023

Figure 3. Schematic of the study design

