Idiopathic PD is characterised by a continuous progression of clinical symptoms and can be preceded by a prodromal phase lasting years or even decades, defined by a specific set of non-motor symptoms such as Rapid Eve Movement (REM) sleep behaviour disorder, depression, constipation, and anxiety. At their onset, motor symptoms are usually unilateral, an asymmetry usually persists through the course of the disease. Bradykinesia, rigidity, and tremor are the typical motor abnormalities of early-stage PD, leading the patient to seek medical attention and guiding the first diagnosis. As the disease progresses, more debilitating symptoms emerge, as motor fluctuations (on/off phases) and dyskinesias manifest (Poewe et al., 2017). Slow walking is a common manifestation of PD that negatively affects patients' performance in daily living activities (Mehrholz et al., 2016; Muslimović et al., 2008). Among the most burdensome characteristics of late-stage PD are instability of posture and gait abnormalities, oftentimes causing falls that can be quite harmful, frequently leading to hospitalisation and reduction in life expectancy ((Verghese et al., 2009, Fasano et al., 2017). Some studies reported that approximately 35% to 90% of PD patients fall at least once a year, with an average rate of 60.5% (Fasano et al., 2017; Pickering et al., 2007; Wood et al., 2002). In another work, it was estimated that roughly 39% of patients sustain multiple falls and fall-related injuries over one year (Allen et al., 2013). Given the high rate of falls during walking in people with PD and the significant burden they impose on quality of life as well as on the health care system, identifying individuals at higher risk and developing rehabilitation programs to reduce such risk is crucial. Motor symptoms are also supplemented by a set of non-motor manifestations which can greatly affect the quality of life of the patients, such as pain, cognitive impairment, apathy and autonomic dysfunction (Chaudhuri and Schapira, 2009).

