4.1.2 Rehabilitation in Parkinson's Disease

The clinical management of PD has traditionally been centred on drug-based therapy (i.e. Levodopa) and surgical approaches (i.e., deep brain stimulation). Nonetheless, despite the undeniable usefulness of such treatments, PD patients still experience progressive motor deterioration and disability largely due to gait, balance and posture impairments (Abbruzzese et al., 2016).

A growing body of evidence highlights the effectiveness of physical therapy in PD and its positive effects on both motor and non-motor complications of PD (Abbruzzese et al., 2016; Tomlinson et al., 2013; van der Kolk and King, 2013). Due to these promising results and the amelioration of quality of

life, physiotherapy rehabilitation programs are currently considered an essential component of the management of patients with PD.

Importantly, rehabilitation was shown to have a positive effect on the risk of fall in a large metanalysis study (Shen et al., 2016), showing a significant overall fall rate reduction over both the short and long term, and supporting the application of exercise training to improve balance and gait ability and ultimately prevent falls in people with PD.

Although the evidence for a positive effect of physiotherapy rehabilitation treatments in PD is increasingly clear, some open questions remain to be further explored. One such question is which type of intervention yields the best results, and for how long the effect persists. Recent studies have shown that some forms of exercise such as balance training, gait training or complementary techniques such as Tai Chi can improve balance and mobility, as well as reduce fall frequency for up to six months after the end of training (Mak et al., 2017). This promising evidence highlights the necessity for structured and regular regimens of physiotherapy rehabilitation for every PD patient, a pressing need that is still unmet, due to the limited availability of physiotherapy practices (Benayoun et al., 2019) and the insufficient access to such services in remote and rural areas (Deane et al., 2002). Consequently, remote and web-based solutions for rehabilitation such as the one offered in this study can close this crucial gap and deliver this indispensable service in a capillary way.

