7.5 Long Term Intervention Period

During Visit 3 patients will be asked whether they want to:

a) continue with their already assigned treatment;

Patients will continue with their respective rehabilitation programs.

b) switch to the other arm;

If patients on the conventional physiotherapy arm would like to start the FeetMe program they will be trained to use the devices and will start their 12 weeks program. Patients of FeetMe group wanting to switch from FeetMe to CPt will need to arrange the care themselves. Patients who switch will have the same visit schedule as during the first three months.

c) discontinue rehabilitation.

If a patient would like to discontinue rehabilitation they will still be asked to remain in the study for further data collection.

7.5.1 Remote Gait Monitoring 2

At the end of Visit 3, all patients will perform a second remote gait monitoring period. All patients will use the insoles remotely while performing their day-to-day activities (including physiotherapy) for 2 weeks. Data will be recorded in standalone mode (without a phone).

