9.5.3 Exploratory analysis

Inferential analysis will not be performed if the smallest group involving in the comparison has a size smaller than 10.

To explore the long term efficacy of FeetMe home-based rehabilitation program compared to conventional physiotherapy in patients who continue to Week 24, the following will be applied:

The change in gait velocity and Stance Time Variability from baseline to week 24 will be compared between the Feetme group and the conventional rehabilitation group using the constrained longitudinal data analysis (cLDA) model or a non-parametric analysis of covariance in case of violation of the assumption of cLDA model, as indicated for the primary objective. The change in these 2 parameters from week 12 to week 24 will be compared using the linear mixed model with an adjustment on the value at week 12 and on the covariable used in the stratified randomisation "conventional physiotherapy in progress". In this model, the centre will be included as a random effect. The rate of falls assessed within 24 weeks will be compared between the two groups using the generalized linear model (GLM with log link function and negative binomial distribution) with the logarithm of duration of patient's follow up (censored at week 24) as offset variable.

All other endpoints will be analysed using descriptive statistics:

- To explore the maintenance of the effect after 3 months in patients who stop physiotherapy at Week 12, the method described previously will be employed for the analysis of the first exploratory objective, namely inferential analysis for the three parameters gait velocity, stance time variability and rate of falls and descriptive analyses for the other endpoints.
- To explore the efficacy in patients who switch from one treatment to the other at Week 12, descriptive analyses will be performed.

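### Section 6.1 claims a within-individual comparison of the two treatments in patients who switch, but with a self-chosen order, no washout and no period reference, treatment is confounded with period; the consequence is minor because these data are exploratory.

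*Protocol*

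**What the plan says.** Protocol section 6.1 ends with a list of what the design is expected to achieve after Week 12. One item is to "compare efficacy of the two treatment within the same individual who decides to switch". The same section, which also lets patients discontinue, describes how switchers arise: "After the Primary Intervention Period patients will be offered to chose how to proceed i.e.: to continue on their original allocation, to switch arms". It adds a qualifier just before the list: "The number of patients on the arms at this point will not be controlled and the data gathered will be exploratory in nature".

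Section 7.5 places the choice at Visit 3, the visit at which the Week 12 gait outcome is measured (section 7.4.3). It describes each direction: "If patients on the conventional physiotherapy arm would like to start the FeetMe program they will be trained to use the devices and will" begin their 12-week program, and "Patients of FeetMe group wanting to switch from FeetMe to CPt will need to arrange the care themselves". No washout is mentioned.

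The formal objective in Table 5.1 is narrower than the bullet: to explore efficacy in patients who switch. The analysis in section 9.5.3 is one sentence: "To explore the efficacy in patients who switch from one treatment to the other at Week 12, descriptive analyses will be performed". It names no reference group and no handling of period.

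Two background statements bear on the point. Section 4.1.1 says that "Idiopathic PD is characterised by a continuous progression of clinical symptoms". Section 4.1.2 reports that some forms of exercise improve balance and mobility and "reduce fall frequency for up to six months after the end of training".

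**The concern.** A within-individual comparison of two treatments suggests a crossover, with each patient as their own control. A crossover supports that reading because order is randomised, carry-over is dealt with, and patients in the opposite order show what the passage of time alone does. Here each switcher has one order, chosen by the patient after 12 weeks on the first treatment. Within that person, treatment and period are the same variable.

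Three other things can then appear as a treatment difference:

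- **Time change.** Progression, or familiarity with the walk test, would have occurred without a switch.
- **Carry-over.** An effect of the first treatment may last into the second 12 weeks.
- **Regression to the mean.** If patients with a poor first-period change switch more often, their second-period change will on average look better whatever they receive.

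At stake is how a descriptive table would be read. A gain after switching could be taken as patient-level evidence for one treatment over the other, on the strength of a design property that the trial does not have.

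**Working it through.** **The plan's own figure.** Section 9.4 uses a difference of 14 cm/s, SD of change 27 cm/s, two-sided alpha 0.05 and 80% power. A two-sample t-test calculation gives 59.4, so 60 per group (power 0.804 at 60), and 60 / (1 - 0.20) = 75 per group. The stated 60 and 75 reproduce. They concern only the randomised Week 12 comparison; no figure is stated for switchers.

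**Inputs for the illustration.** From section 9.4: SD of velocity 27 cm/s and correlation 0.5 between baseline and Week 12. Assumed here: the same SD and correlation for every pair of visits (Baseline, Week 12, Week 24); no treatment effect, time change or carry-over; log-odds of switching linear in the first-period change; just under 30% of patients switching.

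**Step 1: link between the two changes.** Let d1 = Week 12 minus Baseline and d2 = Week 24 minus Week 12, with common SD s and correlation ρ.

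- var(d1) = 2(1 - ρ)s²
- cov(d1, d2) = -(1 - ρ)s²
- slope of d2 on d1 = -(1 - ρ)s² / [2(1 - ρ)s²] = -0.5, whatever ρ is.

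Each 1 cm/s shortfall in the first period thus predicts a 0.5 cm/s gain in the second, and the mean of d2 - d1 among switchers is -1.5 times their mean d1.

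**Step 2: correlation 0.5.** SD(d1) = 27 × √(2 × 0.5) = 27 cm/s. If the odds of switching double per SD of worse d1, switchers average d1 = -12.3 cm/s, which is 12.3 / 27 = 0.456 SD below zero. Their mean d2 is about 0.5 × 12.3 = +6.2 cm/s. The spurious within-person difference is 6.2 + 12.3 = 18.5 cm/s.

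**Step 3: correlation 0.8, same selection.** SD(d1) = 27 × √(2 × 0.2) = 17.1 cm/s. Mean d1 = -0.456 × 17.1 = -7.8 cm/s, and the spurious difference is 1.5 × 7.8 = 11.7 cm/s.

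**Step 4: no selection.** If switching is unrelated to d1, mean d1 and mean d2 are both zero, and so is the spurious difference.

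**Step 5: a different selection model.** Suppose a latent tendency to switch has correlation r with a worse d1, and 20% or 50% of patients switch. The spurious difference in cm/s is:

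| ρ | r | 50% switch | 20% switch |
|---|---|---|---|
| 0.5 | 0.3 | 9.8 | 17.1 |
| 0.5 | 0.5 | 16.2 | 28.3 |
| 0.8 | 0.3 | 6.2 | 10.7 |
| 0.8 | 0.5 | 10.3 | 17.9 |

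The range is 6 to 28 cm/s, against a design effect of 14 cm/s.

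**Time change and carry-over.** The documents give no figure for either, so none is computed. A time change common to all patients goes straight into d2, and the switchers' own data cannot separate it from treatment.

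**The case against.** The strongest reply is that nothing depends on this bullet. Section 6.1 itself calls the data exploratory, the listed objective is only to explore efficacy in switchers, and section 9.5.3 plans no inference for them, although it does for patients who continue or stop. That stands, and it settles the severity. A reader might infer that the trial would falsely declare one treatment better at some inflated error rate, or that the switch objective cannot be addressed at all. The documents support neither reading: no test is planned, and an objective to explore can be met descriptively.

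The strength of selection is also undocumented. The only reason for switching that section 6.1 names is access, for patients in the physiotherapy arm who find no therapist. Nothing says that gait results guide the choice. That stands too: the figures above are conditional. Nor is it safe to say that the artefact exceeds the 14 cm/s design effect. The plan calls its 0.5 correlation conservative, and at 0.8 the main illustration falls below 14.

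On carry-over, the six-month statement concerns balance, mobility and falls after certain exercise types, not gait velocity. Persisting benefit would leave the Week 12 to Week 24 change near zero rather than create an apparent gain. Carry-over is therefore a possibility, not something shown.

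Finally, one might object that the protocol does not separate the two switch directions. It does not say that they are pooled either, and section 9 leaves data displays to the SAP, so this is no fault.

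What survives is that section 6.1 credits the design with a comparison that self-selected switching cannot give. Calling data exploratory does not supply the missing reference, and no later analysis detail can add randomised order or a washout.

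**Conclusion.** The point holds as a minor one. Section 6.1 claims a within-individual comparison of efficacy, but in switchers treatment is confounded with period, and section 9.5.3 provides no period reference. The primary and key secondary results, alpha and the sample size are untouched.

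The possible distortion is about 18.5 cm/s at correlation 0.5 and about 12 cm/s at 0.8 if the odds of switching double per SD of worse first-period change. Under the other selection model it is 6 to 28 cm/s, and with no dependence on the first-period change it is zero. These figures rest on assumed selection and on equal SD and correlation across visits. They illustrate what could happen and do not predict the trial's result.

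**What to change.** In section 6.1, replace the bullet with one saying that the design will describe outcomes after a self-selected switch.

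In section 9.5.3:

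- Present the Week 12 to Week 24 change of switchers, by direction, beside that of patients from the same randomised arm who continued unchanged.
- Keep this descriptive, with Baseline and Week 12 values shown. Give an adjusted difference only where both groups meet the protocol's own minimum of 10.
- Label the result non-randomised and hypothesis-generating. State that the continuers give a period reference and, with Baseline and Week 12 values taken into account, reduce regression to the mean, but do not remove self-selection.
- State that no treatment comparison will be drawn from period 1 versus period 2 within switchers.

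The cost is a few sentences and one exploratory table. All patients who remain in the study attend Visit 4 whatever they choose at Visit 3, so no new data or patients are needed. The trial gives up only a claim that it cannot support.
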